5. TABLE OF EVENTS

Table 3: Table of Events

Year 1 - For all subjects

	Screening Phase	Double-Blind, Placebo-controlled Treatment Phase						Early Termination	Post-Treatment Observational Follow-up Phase
Visit Number	Screening	2 Baseline	3	4-9 Every 4 weeks	10-13 Every 6 weeks	14	15	ET ^a	28
Week	-10 to 0	0	1 ± 3 days	4, 8 ^d , 12, 16 ^d , 20, 24 ± 3 days	30, 36, 42, 48 ± 3 days	52 ± 3 days	53 ^f		4 Weeks After Last Dose (± 3 days)
STUDY ENTRY AND GENERAL ASSESSMENTS									
Main Informed Consent	X	-	-	-	-	-	-	-	-
Inclusion/Exclusion Criteria	X	X	-	-	-	-	-	-	-
Demographics	X	-	-	-	-	-	-	-	-
Complete Medical History	X	-	-	-	-	-	-	-	-
FibroScan ^b	X	-	-	-	-	-	-	-	-
Prior/ Concomitant Medication Evaluation	Continuous starting after the informed consent form is signed through 28 days after end of treatment								
Prior/Concomitant Procedures Evaluation	Continuous starting after the informed consent form is signed through 28 days after end of treatment								
Hemoglobin A1c	X	-	-	-	-	-	-	-	-
Urine EtG Test	X	-	-	Week 24	-	X	-	-	-

Table 3: Table of Events (Continued)

Year 1 - For all subjects

	Screening Phase	Double-Blind, Placebo-controlled Treatment Phase						Early Termination	Post-Treatment Observational Follow-up Phase
Visit Number	Screening	2 Baseline	3	4-9 Every 4 weeks	10-13 Every 6 weeks	14	15	ET ^a	28
Week	-10 to 0	0	1 ± 3 days	4, 8 ^d , 12, 16 ^d , 20, 24 ± 3 days	30, 36, 42, 48 ± 3 days	52 ± 3 days	53 ^f		4 Weeks After Last Dose (± 3 days)
Postmenopausal testing: estradiol and follicle-stimulating hormone (for women 50-55 years with undocumented status)	X	-	-	-	-	-	-	-	-
α-fetoprotein	X	-	-	-	-	-	-	-	-
QuantiFERON [®] -TB Gold Test ^c , Hepatitis B & C and HIV Tests	X	-	-	-	-	-	-	-	-
SAFETY ASSESSMENTS									
Adverse Event Evaluation	Continuous starting after the informed consent form is signed through 28 days after end of treatment.								
Complete Physical Examination	X	-	-	-	-	X	-	X	X
Targeted Physical Examination	-	X	X	X	X	-	X	-	-
Vital Signs and Weight	X	X	X	X	X	X	X	X	X
Height	X	-	-	-	-	-	-	-	-
12-Lead ECG	X	-	-	Weeks 4, 12, 24	-	X	-	X	X
Hematology Panel	X	X	X	X	X	X	X	X	X
Chemistry Panel	X	X	X	X	X	X	X	X	X
PT and INR	X	X	X	X	X	X	-	X	X

Table 3: Table of Events (Continued)
Year 1 - For all subjects

	Screening Phase	Double-Blind, Placebo-controlled Treatment Phase						Early Termination	Post-Treatment Observational Follow-up Phase
Visit Number	Screening	2 Baseline	3	4-9 Every 4 weeks	10-13 Every 6 weeks	14	15	ET ^a	28
Week	-10 to 0	0	1 ± 3 days	4, 8 ^d , 12, 16 ^d , 20, 24 ± 3 days	30, 36, 42, 48 ± 3 days	52 ± 3 days	53 ^f		4 Weeks After Last Dose (± 3 days)
Urinalysis	X	X	-	X	Week 36	X	-	X	X
Urine cytology	X	-	-	Weeks 12, 24	-	X	-	X	X
FOBT	X	-	-	Weeks 12, 24	Weeks 36, 48	-	-	X	X
Serum β-hCG	X	X	-	X	X	X	-	X	X
Urine β-hCG	-	X ^e	-	Weeks 8, 16	-	-	-	-	-
Pregnancy counseling for FCBP	X	X	X	X	X	X	X	X	X
EFFICACY ASSESSMENTS									
Liver biopsy/histology ^f	X ^f	-	-	-	-	-	X ^f	X ^f	-

Table 3: Table of Events (Continued)
Year 1 - For all subjects

	Screening Phase	Double-Blind, Placebo-controlled Treatment Phase						Early Termination	Post-Treatment Observational Follow-up Phase
Visit Number	Screening	2 Baseline	3	4-9 Every 4 weeks	10-13 Every 6 weeks	14	15	ET ^a	28
Week	-10 to 0	0	1 ± 3 days	4, 8 ^d , 12, 16 ^d , 20, 24 ± 3 days	30, 36, 42, 48 ± 3 days	52 ± 3 days	53 ^f		4 Weeks After Last Dose (± 3 days)
PHARMACOKINETIC		ASSESSMENTS							
Blood sample for metabolic tests	-	X	-	Week 24	-	X	-	X	-
INVESTIGATIONAL PRODUCT (IP)									
Dispense IP	-	X ^j	X	X	X	-	-	-	-
Return and Count IP	-	-	X	X	X	X	-	X	-

Table 3: Table of Events (Continued)

Year 2 - For subjects who participate in the active treatment phase:

	Double-Blind, Active Treatment / Extension Phase				Early Termination	Post-Treatment Observational Follow-up Phase
Visit Number	16	17-22 Every 4 weeks	23-26 Every 6 weeks	27 EOT	ET ^a	28
Week	54 ^f	55, 58, 62, 66, 70, 74 ± 3 days	78, 84, 90, 96 ± 3 days	102 ± 3 days		4 Weeks After Last Dose (± 3 days)
SAFETY ASSESSMENTS						
Prior/ Concomitant Medication Evaluation	Continuous starting after the informed consent form is signed through 28 days after end of treatment					
Prior/Concomitant Procedures Evaluation	Continuous starting after the informed consent form is signed through 28 days after end of treatment					
Adverse Event Evaluation	Continuous starting after the informed consent form is signed through 28 days after end of treatment.					
Complete Physical Examination	-	-	-	X	X	X
Targeted Physical Examination	X	X	X	-	-	-
Vital Signs and Weight	X	X	X	X	X	X
12-Lead ECG	-	Weeks 58, 66, 74	Week 84	X	X	X
Hematology Panel	-	X	X	X	X	X
Chemistry Panel	-	X	X	X	X	X
PT and INR	-	X	X	X	X	X
Urinalysis	-	X	Week 84	X	X	X
Urine cytology	-	Weeks 66, 74	-	X	X	X
FOBT	-	Weeks 62, 74	Weeks 84, 96	X	X	X
Serum β-hCG	X	X (except Week 55)	X	X	X	X
Pregnancy counseling for FCBP	X	X	X	X	X	X

Table 3: Table of Events (Continued)

Year 2 - For subjects who participate in the active treatment phase:

	Double-Blind, Active Treatment / Extension Phase				Early Termination	Post-Treatment Observational Follow-up Phase
Visit Number	16	17-22 Every 4 weeks	23-26 Every 6 weeks	27 EOT	ET ^a	28
Week	54 ^f	55, 58, 62, 66, 70, 74 ± 3 days	78, 84, 90, 96 ± 3 days	102 ± 3 days		4 Weeks After Last Dose (± 3 days)
PHARMACOKINETIC [REDACTED]					ASSESSMENTS	
Blood sample for metabolic tests [REDACTED]	-	-	-	X	X	-
INVESTIGATIONAL PRODUCT (IP)						
Dispense IP	X	X	X	-	-	-
Return and Count IP	-	X	X	X	X	-

Abbreviations: β -hCG = beta human chorionic gonadotropin; [REDACTED] ECG = electrocardiogram; [REDACTED] EtG = ethyl glucuronide; EOT = end of treatment; ET = Early Termination Visit; FCBP = females of child bearing potential; FOBT = fecal occult blood test; HCC = hepatocellular cancer; HIV = human immunodeficiency virus; [REDACTED] INR = international normalized ratio; IP = investigational product; [REDACTED] PT = prothrombin time; [REDACTED] TB = tuberculosis.

- ^a Subjects who discontinue the study prior to the Week 52 Visit (subjects who do not participate in the active treatment phase) or the Week 102 Visit (subjects who participate in the active treatment phase) will have an ET Visit. Subjects who discontinue the study prior to the Week 52 will undergo all of the assessments required at the Week 52 Visit and Subjects who discontinue the study after the Week 52 and prior to Week 102 Visit will undergo all of the assessments required at the Week 102 Visit.
- ^b FibroScan can be used to determine eligibility for liver biopsy.
- ^c If a subject has adequate documentation of successful treatment for either latent or active TB, the QuantiFERON-TB Gold test is not needed. Instead, a chest radiograph, obtained within the 12 weeks prior to Screening, without changes suggestive of active TB infection as determined by a qualified radiologist, will be sufficient to permit further participation in the study for these subjects. Documentation of adequate treatment for TB must be obtained prior to randomization.
- ^d Visit 5 Week 8 and Visit 7 Week 16 will be remote visits. Central laboratory tests, target physical examination, vital sign and weight will not be performed during these remote visits. However, if laboratory tests and/or physical examination is needed based on the Investigator's clinical judgement, an unscheduled visit should be performed at the investigational site. Urine pregnancy test kits will be provided to the subjects at Visit 4 Week 4 and Visit 6 Week 12. At Visit 5 Week 8 and Visit 7 Week 16 subjects will perform urine β -hCG test at home. IP will be dispensed at Visit 4/Week 4 and Visit 6/Week 12 for these 2 visits.
- ^e Urine pregnancy test will be performed to assess subject eligibility prior to the first administration of IP if a serum pregnancy test was not obtained within 72 hours prior to dosing (negative results required for IP administration).
- ^f Subjects who do not have a historical biopsy will undergo a liver biopsy procedure for study eligibility. The independent histopathologists will review the liver biopsy specimens to assess whether the subject meets the histological inclusion criteria. Screening liver biopsy will serve as the Baseline assessment. Subjects who discontinue after Week 20 and before Week 52 will undergo a liver biopsy procedure at ET Visit. IP should be stopped 7-10 days prior to Week 53 or ET Visit biopsy and restarted 7 days after biopsy at Week 54 if subjects participate in the active treatment phase.

^j First dose of IP should be administered at the investigative site.

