Approximately 180 adult male and female subjects with a confirmed diagnosis of NASH and Stage 2 or Stage 3 fibrosis based upon the NASH Clinical Research Network (CRN) Histologic Scoring System and a NAS of 4 or higher, with a score of at least 1 for each of the three components (steatosis, hepatocellular ballooning, and lobular inflammation), will be randomized 1:1:1 to treatment with oral CC-90001 (200 mg QD, 60 subjects; 400 mg QD, 60 subjects) or matching placebo (60 subjects) for 52 weeks. Prior to the implementation of Protocol Amendment 4, subjects were also randomized into a 100 mg QD dose group. The subjects who were previously randomized to the 100 mg dose group will remain in the 100 mg dose group throughout the study. It is expected that approximately 10-15 subjects will have been randomized to the 100 mg group at time of implementation of Protocol Amendment 4. Thus, a total of approximately 195 subjects will participate in the study.

Randomization will be stratified by liver fibrosis stage (Stage 2/Stage 3) and by the presence of Type 2 Diabetes Mellitus (DM) (yes/no). Approximately 60 subjects with Stage 2 or Stage 3 fibrosis will be enrolled per treatment arm. To ensure enrollment of a suitable number of subjects with Stage 3 fibrosis, up to 15 subjects with Stage 2 fibrosis may be enrolled per arm. Randomization to one stratum will be halted once the enrollment target is achieved for that stratum. Randomization, treatment assignment and stratification will be managed by an interactive web response system (IWRS).

An independent external data monitoring committee (DMC) will be responsible for review of the interim analyses data and will make recommendations to the Sponsor, who will be responsible for final decision-making. An unblinded interim analysis will be performed after approximately 50% of subjects complete 52 weeks of the placebo-controlled treatment phase (as described in the DMC Charter). The DMC will review the totality of the available data to determine the following options:

- Continue the study as planned
- Terminate the study for futility
- Stop enrolling a treatment arm due to futility if not fully enrolled at interim analysis

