6.2. Treatment Period

The subject will begin treatment upon confirmation of eligibility. For all subsequent visits, an administrative window of ± 3 days is permitted except Visit 15/Week 53 and Visit 16/Week 54 (for the subjects who participate in the active treatment phase). Visit 15/Week 53 should be performed 7 to 10 days after Visit 14/Week 52 and Visit 16/Week 54 (for the subjects who participate in the active treatment phase) should be performed 7 to 10 days after Visit 15/Week 53. Scheduling of Visits 3 to 14 is based on Visit 2/Week 0 (randomization date) and scheduling of Visits 17 to 27 (for the subjects who participate in the active treatment phase) is based on Visit 16/Week 54 (re-randomization date). 

Visit 5 Week 8 and Visit 7 Week 16 will be remote visits. Assessments performed at these visits have been specified in the Table of Events, [Table 3](#)

The following evaluations will be performed at the frequency specified in the Table of Events, [Table 3](#). The evaluations should be performed prior to dosing on the visit day, unless otherwise specified.

- Adverse event evaluation (continuously)
- Concomitant medications evaluation (continuously)
- Concomitant procedures evaluation (continuously)
- Counseling about pregnancy precautions and the potential risks of fetal exposure
- Complete physical examination (Section 6.5.1)
- Targeted physical examination (Section 6.5.1)
- Vital signs and weight (Section 6.1)

- 12-lead ECG (Section 6.5.2)
- Clinical Laboratory Evaluations (Section 6.5.3):
 - Hematology panel
 - Coagulation tests
 - Chemistry panel
 - Urinalysis and urine cytology
 - Serum pregnancy test
 - Urine pregnancy test at Visit 5 Week 8 and Visit 7 Week 16
 - Urine EtG test
 - Fecal occult blood test (FOBT)
- Efficacy assessment (Section 6.6):
 - Liver biopsy/histology

- Investigational product (IP) dispensation: The Principal Investigator, Sub-investigator, or Study Coordinator should make an effort to witness subjects taking their first dose and record the date and time in the source document record. Subjects are instructed to take 3 tablets of IP QD, approximately the same time of day (preferably in the morning), with or without food. Visit 5/Week 8 and Visit 7/Week 16 will be remote visits and IP will be dispensed at Visit 4/Week 4 and Visit 6/Week 12 for these 2 visits.
- Investigational product (IP) return (all used and unused blister cards) and IP compliance assessment (Section 7.6)

6.2.1. **Unscheduled Visits**

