9.7. Safety Analysis

The safety analyses will be performed using the safety population, defined as all subjects who are randomized and receive at least one dose of investigational product.

Safety will be assessed by clinical review of all relevant parameters including treatment emergent adverse events (TEAEs), laboratory tests, vital signs, and ECG; no inferential testing for statistical significance will be performed. Data from safety assessments will be summarized descriptively for the Placebo-controlled Phase (Weeks 0 to 52) by the treatment group of CC-

90001 100 mg, 200 mg QD, 400 mg QD, and placebo; and for the CC-90001 Exposure Phase for subjects who receive at least one dose of CC-90001 treatment. For all safety analyses baseline will be relative to the first dose date following randomization at Week 0.

Adverse events will be classified using the MedDRA classification system. All TEAEs will be summarized by system organ class, preferred term, severity and relationship to investigational product. The TEAEs leading to death or to discontinuation from treatment and serious adverse events will be summarized and listed separately.

Data from other safety assessments will be summarized descriptively. Shift tables for laboratory parameters showing the number of subjects with values low, normal, and high comparing with the normal reference ranges pre-treatment versus post treatment will be provided.

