inflammatory bowel disease and the subjects with a history of bleeding peptic ulcer or bleeding diverticular disease within 5 years. Furthermore, the protocol also implemented FOBT at Screening and approximately every 12 weeks during the study and discontinuation criteria for the subject with positive FOBT in the study. With all these in place the occurrence of GI bleeding in the study continues to be well monitored to ensure safety of subjects over the course of the trial.

- Sections affected

Study Population (Section 4), Table of Events (Section 5), and Procedures – Screening Phase (Section 6.1)

- **Condition of worsening liver function was changed**

- The values of alanine aminotransferase (ALT)/ aspartate aminotransferase (AST) fluctuate over the short period of time as well as over the course of NASH disease. More than 20% increase of ALT or AST value in the subjects with ALT or AST less than 3 X upper limit of normal (ULN) may not be an evidence of worsening of liver function. In addition, throughout the study hepatotoxicity is monitored and subjects are to be discontinued if liver biochemistry abnormalities meet the discontinuation criteria (Appendix C). Therefore, the protocol was revised that another measurement is obtained, at least 4 weeks apart, only in the subjects with screening ALT or AST greater than 3 X ULN. If retested ALT or AST increase more than 20% the subject will be excluded from study.

- Sections affected

Procedures – Screening Phase (Section 6.1) and Appendix C

- **Approved weight-loss medications were removed from prohibited medications**

- Exclusion criterion #12 was removed and inclusion criterion # 6 was revised to allow anti-obesity medications in the study if the medications have been stable for 3 months prior to Screening or historical biopsy used for Screening.

- Sections affected

Study Population (Section 4) and Concomitant Medications and Procedures (Section 8)

- **Changed Visit 5 Week 8 and Visit 7 Week 16 to remote visit**

- Visit 5 Week 8 and Visit 7 Week 16 were changed to remote visit to reduce operational complexity and the burden for the subjects.

- Sections affected

Table of Events (Section 5) and Procedures (Section 6)

The amendment also includes other minor clarifications and corrections.

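### Subjects who reached Weeks 8 and 16 before Amendment 4 (concentrated in the 100 mg arm), and placebo crossovers, have up to two more scheduled checks than later subjects; the safety tables make no allowance for this

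*Combined protocol and SAP*

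**What the plan says.** **Current Year 1 schedule.** Table 3 is headed "Year 1 - For all subjects". Its grid marks hematology, chemistry, PT/INR, vital signs, weight and targeted examination for Visits 4-9, but footnote d takes two of those visits out: "Central laboratory tests, target physical examination, vital sign and weight will not be performed during these remote visits". If the investigator judges that tests or an examination are needed, "an unscheduled visit should be performed at the investigational site".

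**Before Amendment 4.** The justification for that amendment records that "Visit 5 Week 8 and Visit 7 Week 16 were changed to remote visit to reduce operational complexity and the burden for the subjects". The earlier visit table is not in the documents.

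**Year 2.** The visit weeks are "55, 58, 62, 66, 70, 74 ± 3 days", then 78, 84, 90, 96 and 102. Hematology, chemistry and PT/INR are marked at all of them, and no remote-visit footnote applies. Section 6.2 times these visits from Week 54, when placebo subjects are re-randomized to active drug.

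**The 100 mg arm.** Section 3.1: "It is expected that approximately 10-15 subjects will have been randomized to the 100 mg group at time of implementation of Protocol Amendment 4". No one is randomized to it afterwards. Placebo, 200 mg and 400 mg continue to 60 each.

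**Analysis.** Section 9.7: "Data from safety assessments will be summarized descriptively for the Placebo-controlled Phase (Weeks 0 to 52) by the treatment group", with 100 mg, 200 mg, 400 mg and placebo side by side. A second summary covers the CC-90001 Exposure Phase for everyone who took at least one dose of CC-90001. Shift tables compare values before and after treatment. There is no inferential testing, and nothing is said about subjects having followed different visit schedules.

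**The concern.** A count of subjects with an abnormal value at any time on treatment rises with the number of scheduled looks, even when true incidence is the same. Sections 6.5.1, 6.5.3 and 10.3 turn clinically significant examination and laboratory findings after the first dose into adverse events, so TEAE counts can move in the same direction.

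Two groups are looked at more often early on drug. One is subjects who reached Week 8 or 16 while those visits were still on site. The 100 mg arm should hold a larger share of them than any other arm, because it closed when Amendment 4 took effect. The other is placebo subjects who cross over in Year 2.

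The lowest dose could then look somewhat worse than it is beside placebo and the higher doses. This matters in a dose-finding trial because Section 9.3 says that the overall choice of minimum effective dose will also account for safety endpoints. In the Exposure Phase summary, subjects with closer early checks are pooled with subjects who had wider gaps.

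**Working it through.** The plan states no figure on this point, so there is nothing to reproduce. The check rebuilds the laboratory schedule and asks how often a short abnormality would be caught.

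**1. Scheduled draws, in weeks on drug (Table 3, footnote d, Section 6.2)**
- Full (inferred pre-Amendment 4) Year 1: 1, 4, 8, 12, 16, 20, 24, 30, 36, 42, 48, 52, which is 12 draws.
- Current Year 1: the same without 8 and 16, which is 10 draws.
- Crossovers, Year 2 week minus 54: 1, 4, 8, 12, 16, 20, 24, 30, 36, 42, 48. That is 11 draws in 48 weeks, against 9 on the current Year 1 schedule.

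The current schedule has 8-week gaps at Weeks 4-12 and 12-20 where the full one has 4-week gaps.

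**2. Detection.** Assume an abnormality lasting L weeks with onset uniform over a window, found if a scheduled draw falls within it. For onset in Weeks 4-20 (16 weeks), the full schedule has four draws (8, 12, 16, 20) and the current one has two (12, 20). Detection is min(1, 4L/16) on the full schedule and min(1, 2L/16) on the current one.

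**3. Arm mix.** Take all 100 mg subjects on the full schedule, and 10 to 15 of 60 in each other arm. The latter share is an assumption (equal concurrent allocation); the documents do not give it. Detection in the other arms is s × full + (1 − s) × current, with s = 10/60 to 15/60.

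| Onset window | L (weeks) | Full | Current | Other arms | Ratio, 100 mg : other |
|---|---|---|---|---|---|
| 4-20 | 2 | 50% | 25% | 29-31% | 1.6-1.7 |
| 4-20 | 4 | 100% | 50% | 58-63% | 1.6-1.7 |
| 4-20 | 6 | 100% | 75% | 79-81% | 1.23-1.26 |
| 4-20 | 8 | 100% | 100% | 100% | 1.0 |
| 0-52 | 2 | 44% | 37% | 38% | 1.15-1.17 |
| 0-52 | 4 | 85% | 69% | 72-73% | 1.16-1.18 |
| 0-52 | 6 | 100% | 92% | 94% | 1.06-1.07 |
| 0-52 | 8 | 100% | 100% | 100% | 1.0 |

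**4. If only a share f of 100 mg subjects had both extra draws.** For L up to 4 and onset in Weeks 4-20, full detection is twice current detection. The ratio is then (1 + f) / (1 + f × s):
- f = 1: 2/1.167 = 1.71 to 2/1.25 = 1.60
- f = 0.5: 1.5/1.083 = 1.38 to 1.5/1.125 = 1.33
- f = 0: 1.0

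**5. In subjects.** Assume true incidence in Weeks 4-20 of 5% to 20%. The excess found in the 100 mg arm is n × incidence × (full − other arms):
- n = 10, 5%, L = 2: 10 × 0.05 × (0.500 − 0.292) = 0.1 subject
- n = 15, 20%, L = 4: 15 × 0.20 × (1.000 − 0.625) = 1.1 subjects

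**6. Crossovers against subjects on the current Year 1 schedule.** For onset in Weeks 0-48 on drug the detection ratio is 1.22-1.25 for L of 1 to 4 weeks, 1.09 for 6 weeks and 1.0 for 8 weeks. This part follows from the current Table 3 alone.

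**The case against.** The best case against runs as follows.

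- **The schedule turns on visit date, not randomization date.** A reader might infer that every 100 mg subject had the extra checks because all were randomized before Amendment 4. The documents do not support that. The current Year 1 table covers all subjects without exemption, so a 100 mg subject who had not yet reached Week 8 or 16 at implementation would lose that check. No dates are given. This stands, and the ratios above are upper values.
- **The earlier schedule is not shown.** Laboratory draws at Weeks 8 and 16 before the amendment are a fair inference from the change to remote visits, but only an inference. This stands.
- **The 1.6-1.7 ratio covers a window the plan does not report.** Section 9.7 reports Weeks 0 to 52, where the figure is about 1.15-1.18 for 2- to 4-week episodes and fades to nothing at 8 weeks. This stands.
- **The summaries are descriptive, and their metric is not fixed.** Summaries by visit would not be affected. Detail is deferred to a separate SAP that is not in the supplied text. Adverse events are collected continuously, and unscheduled visits would catch some cases under either schedule. This softens the point, but shift tables and TEAE incidence still depend on how often subjects are checked.
- **The Exposure Phase pools crossovers; it does not compare them with originally randomized subjects.** This is correct. The effect there is on the pooled rate, not on a planned contrast.

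What remains is that Section 9.7 sets 100 mg beside arms with a different mix of schedules and makes no provision for it.

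**Conclusion.** The point holds in limited form. Subjects seen at Weeks 8 and 16 before the amendment, and placebo crossovers, have more scheduled early checks than subjects on the current Year 1 schedule. Abnormalities shorter than 8 weeks are more likely to be found in them at equal incidence. For 100 mg against the full other arms, the inflation over Weeks 0-52 is at most about 1.15-1.18 times for episodes of up to 4 weeks, or about one subject or fewer among 10-15.

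This rests on four assumptions: on-site laboratory draws at both visits before Amendment 4; 10-15 of 60 subjects in each other arm on that schedule; uniform onset; and 5-20% incidence in Weeks 4-20 for the subject count.

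A reader might go further and infer that the randomized safety comparison as a whole is biased. It is not. The change reached placebo, 200 mg and 400 mg at the same calendar time, so those arms share the same schedule mix in expectation and their contrasts are unaffected. The exposed comparisons are the small, closed 100 mg arm against the full arms, and any reading of crossover data beside Year 1 data.

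**What to change.** In Section 9.7 and the SAP:

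1. Keep the all-data safety tables primary. No result leaves them.
2. Show 100 mg laboratory, vital-sign, shift and TEAE incidence beside placebo, 200 mg and 400 mg subjects randomized before Amendment 4, as well as beside the full arms. In expectation these concurrent groups share whatever schedule mix the 100 mg arm had, so the comparison works without knowing how many subjects were affected. State the cut-off used to define them.
3. Add a sensitivity table on common visits. In Year 1 it leaves out scheduled Week 8 and 16 results. In the Exposure Phase it leaves out, for placebo crossovers only, the Week 62 and 70 laboratory, vital-sign and examination results. Subjects on CC-90001 since Week 0 keep those visits, which for them are late exposure. The fecal occult blood test is kept throughout, because it runs on its own schedule with no Week 8 or 16 test in Year 1.
4. Add one sentence recording that the visit schedule changed.

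The cost is some wording, extra columns and one further set of tables. The concurrent groups will be small, about 10-15 per arm if allocation was equal, so their percentages will be imprecise. Nothing changes in visits or monitoring.
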